#### **Diarrhea/Colitis:**

Subjects should be carefully monitored for signs and symptoms of enterocolitis (such as diarrhea, abdominal pain, blood or mucus in stool, with or without fever) and of bowel perforation (such as peritoneal signs and ileus).

All subjects who experience diarrhea/colitis should be advised to drink liberal quantities of clear fluids. If sufficient oral fluid intake is not feasible, fluid and electrolytes should be substituted via IV infusion. For Grade 2 or higher diarrhea, consider GI consultation and endoscopy to confirm or rule out colitis.

For **Grade 2 diarrhea/colitis** that persists greater than 3 days, administer oral corticosteroids. For **Grade 3 or 4 diarrhea/colitis** that persists > 1 week, treat with intravenous steroids followed by high dose oral steroids.

When symptoms improve to Grade 1 or less, steroid taper should be started and continued over no less than 4 weeks.

**Type 1 diabetes mellitus (if new onset, including diabetic ketoacidosis [DKA]) or ≥ Grade 3 Hyperglycemia, if associated with ketosis (ketonuria) or metabolic acidosis (DKA)**

For **T1DM** or **Grade 3-4 Hyperglycemia**

Insulin replacement therapy is recommended for Type I diabetes mellitus and for Grade 3-4 hyperglycemia associated with metabolic acidosis or ketonuria.

Evaluate patients with serum glucose and a metabolic panel, urine ketones, glycosylated hemoglobin, and C-peptide.

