#### 5.2.1.2 Dose Modification and toxicity management for immune-related AEs associated with pembrolizumab and combination therapy

Adverse events (both non-serious and serious) associated with pembrolizumab exposure, including coadministration with additional compounds, may represent an immunologic etiology. These adverse events may occur shortly after the first dose or several months after the last dose of treatment and may affect more than one body system simultaneously. Therefore, early recognition and initiation of treatment is critical to reduce complications. Based on existing clinical study data, most irAEs were reversible and could be managed with interruptions of pembrolizumab/combination treatment, administration of corticosteroids and/or other supportive care. For suspected irAEs, ensure adequate evaluation to confirm etiology or exclude other causes. Additional procedures or tests such as bronchoscopy, endoscopy, skin biopsy may be included as part of the evaluation. Dose modification and toxicity management guidelines for irAEs associated with pembrolizumab/combination treatment are provided in Table 3 below.

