#### **Pneumonitis:**

For **Grade 2 events**, treat with systemic corticosteroids. When symptoms improve to Grade 1 or less, steroid taper should be started and continued over no less than 4 weeks.

For **Grade 3-4 events**, immediately treat with intravenous steroids. Administer additional anti-inflammatory measures, as needed.

Add prophylactic antibiotics for opportunistic infections in the case of prolonged steroid administration.

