**Hypophysitis:**

For **Grade 2** events, treat with corticosteroids. When symptoms improve to Grade 1 or less, steroid taper should be started and continued over no less than 4 weeks. Replacement of appropriate hormones may be required as the steroid dose is tapered.

For **Grade 3-4** events, treat with an initial dose of IV corticosteroids followed by oral corticosteroids. When symptoms improve to Grade 1 or less, steroid taper should be started and continued over no less than 4 weeks. Replacement of appropriate hormones may be required as the steroid dose is tapered.

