**Grade 3-4 hyperthyroidism**

Treat with an initial dose of IV corticosteroid followed by oral corticosteroids. When symptoms improve to Grade 1 or less, steroid taper should be started and continued over no

less than 4 weeks. Replacement of appropriate hormones may be required as the steroid dose is tapered.

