**Hepatic:**

For **Grade 2** events, monitor liver function tests more frequently until returned to baseline values (consider weekly).

Treat with IV or oral corticosteroids

For **Grade 3-4** events, treat with intravenous corticosteroids for 24 to 48 hours.

When symptoms improve to Grade 1 or less, a steroid taper should be started and continued over no less than 4 weeks.

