**Renal Failure or Nephritis:**

For **Grade 2** events, treat with corticosteroids.

For **Grade 3-4** events, treat with systemic corticosteroids.

When symptoms improve to Grade 1 or less, steroid taper should be started and continued over no less than 4 weeks.

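### The colitis guidance in Section 5.4.1 starts steroids later for Grade 3-4 events than for Grade 2 events

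*Combined protocol and SAP*

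**What the plan says.** The Diarrhea/Colitis paragraph of Section 5.4.1 has two steroid rules, each tied to how long the event has lasted. A Grade 2 event "that persists greater than 3 days, administer oral corticosteroids". The severe grades follow: "For Grade 3 or 4 diarrhea/colitis that persists > 1 week, treat with intravenous steroids followed by high dose oral steroids". The same paragraph asks sites to watch for signs of bowel perforation, to give fluids, and to consider gastroenterology consultation and endoscopy from Grade 2 upwards.

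Section 5.2.1.2 sets the general principle for immune-related events: "early recognition and initiation of treatment is critical to reduce complications". Table 3 in that section holds pembrolizumab for Grade 2-3 colitis and stops it permanently for Grade 4. It mentions corticosteroids only as a limit on tapering (10 mg or less of prednisone or equivalent per day within 12 weeks), not as a time to start them.

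Section 5.4.1 presents its measures as suggestions, to be applied when the investigator considers the event related to pembrolizumab. Sections 5.3 and 5.3.1 leave supportive treatment to the investigator's judgment.

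**The concern.** A more severe event should not wait longer for treatment than a milder one, yet the colitis paragraph says the reverse. Its Grade 3-4 sentence is the protocol's only written steroid trigger for severe colitis. A site that relies on it would start steroids later in the sicker patient unless the investigator overrides the guidance. The paragraph also does not say which threshold applies when a Grade 2 event worsens to Grade 3 or 4.

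What is at stake is patient safety in a toxicity that can be life-threatening. The point does not touch the sample size, the response endpoint, the toxicity discontinuations or the 12-week limits in Table 3.

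**Working it through.** No statistical figure is involved, so the check compares the texts directly.

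**1. The two triggers in the colitis paragraph**

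- Grade 2: more than 3 days, oral steroids.
- Grade 3-4: more than 1 week = 7 days, IV steroids and then high-dose oral steroids.
- Difference: 7 − 3 = 4 days. Ratio: 7 / 3 ≈ 2.3.

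Between day 3 and day 7 of a persisting event, the text calls for steroids at Grade 2 and for none at Grade 3-4.

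**2. The other Grade 3-4 steroid rules in Section 5.4.1**

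| Condition | Grade 2 steroid rule | Grade 3-4 steroid rule | Wait at Grade 3-4 |
|---|---|---|---|
| Diarrhea/colitis | Oral, after more than 3 days | IV then oral, after more than 1 week | Yes |
| Pneumonitis | Yes, no wait | "immediately treat with intravenous steroids" | None; told to act at once |
| Hypophysitis | Yes, no wait | "treat with an initial dose of IV corticosteroids followed by oral corticosteroids" | None stated |
| Hyperthyroidism | None (beta-blockers suggested) | "Treat with an initial dose of IV corticosteroid followed by oral corticosteroids" | None stated |
| Hepatic | Yes, no wait | "treat with intravenous corticosteroids for 24 to 48 hours" | None stated |
| Renal failure or nephritis | Yes, no wait | "For Grade 3-4 events, treat with systemic corticosteroids" | None stated |

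Colitis is 1 of 6 with a waiting period at Grade 3-4, and the only one where the Grade 3-4 steroid trigger comes later than the Grade 2 action. Of the other 5, 1 demands immediate treatment and 4 set no timing condition. Four of those 5 also have a Grade 2 steroid rule, none with a wait. Table 4 is not counted: it lists corticosteroids only as an option for Grade 3-4 infusion reactions, also without a wait.

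**3. Does any other text correct or explain the order?**

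- Table 3 and its notes give no steroid start time.
- Table 6 (Section 7.2.4) describes Grade 4 as calling for urgent intervention. That conflicts with a one-week condition covering Grade 4 colitis.
- One could read the 3-day oral rule as covering all grades, with one week governing only the move to IV treatment. The wording does not support this. The consultation and endoscopy sentence applies from Grade 2 upwards, whereas the oral steroid sentence names Grade 2 alone.
- Time to exclude infection does not explain it. Section 5.4.1 asks for other causes to be ruled out in every disorder, yet no other Grade 3-4 rule has a wait, and Grade 2 colitis waits only 3 days.

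**The case against.** The strongest reply is that nothing in the protocol forbids earlier steroids. The guidance is only suggested, and Sections 5.3, 5.3.1 and 5.4.1 all defer to the investigator. The drug hold or stop, fluids and work-up carry no wait. Table 6 associates Grade 3 with hospitalization and Grade 4 with urgent intervention, so such a patient is likely to be under close care. On this view delay occurs only if an investigator puts a suggested line above clinical judgment. This stands as a limit: the text does not compel delay. It does not make the default right, because guidance is written to be relied on.

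A second reply concerns the comparison across organs. Colitis is also the only condition with a wait at Grade 2, so the protocol treats it differently throughout, and the other rules cannot prove that no wait at all is correct. This is fair. The firmest evidence is the order within the paragraph itself, which the comparison supports but does not replace.

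Third, deleting the wait altogether goes further than the documents strictly prove. It would call for IV steroids in any drug-related Grade 3 event however brief, with a taper of at least 4 weeks that must fit Table 3's 12-week limit. This also has weight. The exact timing is a clinical decision; the requirement that Grade 3-4 wait no longer than Grade 2 is not in doubt.

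**Conclusion.** The concern holds. As written, the steroid trigger for diarrhea/colitis is inverted with respect to severity: more than 3 days at Grade 2 against more than 7 days at Grade 3-4, a gap of 4 days in the wrong direction. It contradicts the protocol's own principle of early treatment and is out of line with its five other Grade 3-4 steroid rules.

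The conclusion rests on the plain reading that the two sentences are separate, grade-specific rules. It does not assume that sites will follow them against clinical judgment, and the documents give no basis for estimating how often a delay would occur or what harm would follow. It must be corrected because the written default is wrong for a serious toxicity of the study drug.

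**What to change.** Remove the one-week persistence condition from the Grade 3-4 sentence, so that IV steroids followed by high-dose oral steroids apply to Grade 3 or 4 diarrhea/colitis once the investigator judges it related to pembrolizumab, as in the other five rules. If the sponsor's medical lead prefers to keep some observation time, it must not exceed the 3 days used at Grade 2. Add a sentence stating that an event which worsens to Grade 3 or 4 follows the Grade 3-4 rule at once. The medical lead should confirm the final wording and alert sites while the amendment is pending; the existing text already lets investigators treat sooner.

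The cost is one amended paragraph, the IRB review that Section 10.3 requires for protocol changes, and one notice to sites. No extra visits, staff or analysis are needed. The downside is possibly some earlier steroid use in severe colitis. The steps of seeking other causes and judging relatedness stay in place.

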**Hypophysitis:**

For **Grade 2** events, treat with corticosteroids. When symptoms improve to Grade 1 or less, steroid taper should be started and continued over no less than 4 weeks. Replacement of appropriate hormones may be required as the steroid dose is tapered.

For **Grade 3-4** events, treat with an initial dose of IV corticosteroids followed by oral corticosteroids. When symptoms improve to Grade 1 or less, steroid taper should be started and continued over no less than 4 weeks. Replacement of appropriate hormones may be required as the steroid dose is tapered.

**Hyperthyroidism or Hypothyroidism:**

Thyroid disorders can occur at any time during treatment. Monitor patients for changes in thyroid function (at the start of treatment, periodically during treatment, and as indicated based on clinical evaluation) and for clinical signs and symptoms of thyroid disorders.

**Grade 2 hyperthyroidism events (and Grade 2-4 hypothyroidism):**

In hyperthyroidism, non-selective beta-blockers (e.g. propranolol) are suggested as initial therapy.

In hypothyroidism, thyroid hormone replacement therapy, with levothyroxine or liothyronine, is indicated per standard of care.

**Grade 3-4 hyperthyroidism**

Treat with an initial dose of IV corticosteroid followed by oral corticosteroids. When symptoms improve to Grade 1 or less, steroid taper should be started and continued over no

less than 4 weeks. Replacement of appropriate hormones may be required as the steroid dose is tapered.

**Hepatic:**

For **Grade 2** events, monitor liver function tests more frequently until returned to baseline values (consider weekly).

Treat with IV or oral corticosteroids

For **Grade 3-4** events, treat with intravenous corticosteroids for 24 to 48 hours.

When symptoms improve to Grade 1 or less, a steroid taper should be started and continued over no less than 4 weeks.

**Renal Failure or Nephritis:**

For **Grade 2** events, treat with corticosteroids.

For **Grade 3-4** events, treat with systemic corticosteroids.

When symptoms improve to Grade 1 or less, steroid taper should be started and continued over no less than 4 weeks.

**Dose modification and toxicity management of infusion-reactions related to pembrolizumab**

Pembrolizumab may cause severe or life-threatening infusion-reactions including severe hypersensitivity or anaphylaxis. Signs and symptoms usually develop during or shortly after drug infusion and generally resolve completely within 24 hours of completion of infusion. Dose modification and toxicity management guidelines on pembrolizumab associated infusion reaction are provided in Table 4.

**Table 4. Infusion Reaction Treatment Guidelines**

NCI CTCAE Grade	Treatment	Premedication at subsequent dosing
Grade 1 Mild reaction; infusion interruption not indicated; intervention not indicated	Increase monitoring of vital signs as medically indicated until the subject is deemed medically stable in the opinion of the investigator.	None
Grade 2 Requires infusion interruption but responds promptly to symptomatic treatment (e.g., antihistamines, NSAIDS, narcotics, IV fluids); prophylactic medications indicated for $\leq 24$ hrs	Stop Infusion and monitor symptoms. Additional appropriate medical therapy may include but is not limited to: IV fluids Antihistamines NSAIDS Acetaminophen Narcotics	Subject may be premedicated 1.5h ( $\pm$ 30 minutes) prior to infusion of pembrolizumab (MK-3475) with:  Diphenhydramine 50 mg po (or equivalent dose of antihistamine).

NCI CTCAE Grade	Treatment	Premedication at subsequent dosing
	
Increase monitoring of vital signs as medically indicated until the subject is deemed medically stable in the opinion of the investigator.
 
If symptoms resolve within one hour of stopping drug infusion, the infusion may be restarted at 50% of the original infusion rate (e.g., from 100 mL/hr to 50 mL/hr). Otherwise dosing will be held until symptoms resolve and the subject should be premedicated for the next scheduled dose.
 
Subjects who develop Grade 2 toxicity despite adequate premedication should be permanently discontinued from further trial treatment administration.
	Acetaminophen 500-1000 mg po (or equivalent dose of antipyretic).

Grades 3 or 4
 
Grade 3: Prolonged (i.e., not rapidly responsive to symptomatic medication and/or brief interruption of infusion); recurrence of symptoms following initial improvement; hospitalization indicated for other clinical sequelae (e.g., renal impairment, pulmonary infiltrates)
 
Grade 4: Life-threatening; pressor or ventilatory support indicated
	
Stop Infusion.
 
Additional appropriate medical therapy may include but is not limited to:
 
 
IV fluids
 
Antihistamines
 
NSAIDS
 
Acetaminophen
 
Narcotics
 
Oxygen
 
Pressors
 
Corticosteroids
 
Epinephrine
 
 
Increase monitoring of vital signs as medically indicated until the subject is deemed medically stable in the opinion of the investigator.
 
Hospitalization may be indicated.
 
Subject is permanently discontinued from further trial treatment administration.
	No subsequent dosing
Appropriate resuscitation equipment should be available in the room and a physician readily available during the period of drug administration.		

NCI CTCAE Grade	Treatment	Premedication at subsequent dosing

## 5.5 Diet/Activity/Other Considerations

### 5.5.1 Diet

Subjects should maintain a normal diet unless modifications are required to manage an AE such as diarrhea, nausea or vomiting.

### 5.5.2 Contraception

Pembrolizumab may have adverse effects on a fetus in utero.

For this trial, male subjects will be considered to be of non-reproductive potential if they have azoospermia (whether due to having had a vasectomy or due to an underlying medical condition).

Female subjects will be considered of non-reproductive potential if they are either:

- (1) postmenopausal (defined as at least 12 months with no menses without an alternative medical cause; in women < 45 years of age a high follicle stimulating hormone (FSH) level in the postmenopausal range may be used to confirm a post-menopausal state in women not using hormonal contraception or hormonal replacement therapy. In the absence of 12 months of amenorrhea, a single FSH measurement is insufficient.);

OR

- (2) have had a hysterectomy and/or bilateral oophorectomy, bilateral salpingectomy or bilateral tubal ligation/occlusion, at least 6 weeks prior to screening;

OR

- (3) has a congenital or acquired condition that prevents childbearing.

Female subjects of reproductive potential must agree to avoid becoming pregnant while receiving study drug and for 120 days after the last dose of study drug by complying with one of the following:

- (1) practice abstinence† from heterosexual activity;

OR

- (2) use (or have their partner use) acceptable contraception during heterosexual activity.

Acceptable methods of contraception are‡:

Single method (one of the following is acceptable):

- intrauterine device (IUD)
- vasectomy of a female subject's male partner

RUTGERS | eIRB  
APPROVED

IRB ID: Pro20170001392  
Approval Date: 2/22/2023  
Expiration Date: 5/10/2023

- contraceptive rod implanted into the skin

Combination method (requires use of two of the following):

- diaphragm with spermicide (cannot be used in conjunction with cervical cap/spermicide)
- cervical cap with spermicide (nulliparous women only)
- contraceptive sponge (nulliparous women only)
- male condom or female condom (cannot be used together)
- hormonal contraceptive: oral contraceptive pill (estrogen/progestin pill or progestin-only pill), contraceptive skin patch, vaginal contraceptive ring, or subcutaneous contraceptive injection

†Abstinence (relative to heterosexual activity) can be used as the sole method of contraception if it is consistently employed as the subject's preferred and usual lifestyle and if considered acceptable by local regulatory agencies and ERCs/IRBs. Periodic abstinence (e.g., calendar, ovulation, sympto-thermal, post-ovulation methods, etc.) and withdrawal are not acceptable methods of contraception.

‡If a contraceptive method listed above is restricted by local regulations/guidelines, then it does not qualify as an acceptable method of contraception for subjects participating at sites in this country/region.

Subjects should be informed that taking the study medication may involve unknown risks to the fetus (unborn baby) if pregnancy were to occur during the study. In order to participate in the study subjects of childbearing potential must adhere to the contraception requirement (described above) from the day of study medication initiation (or 14 days prior to the initiation of study medication for oral contraception) throughout the study period up to 120 days after the last dose of trial therapy. If there is any question that a subject of childbearing potential will not reliably comply with the requirements for contraception, that subject should not be entered into the study.

### 5.5.3 Use in Pregnancy

If a subject inadvertently becomes pregnant while on treatment with pembrolizumab, the subject will immediately be removed from the study. The site will contact the subject at least monthly and document the subject's status until the pregnancy has been completed or terminated. The outcome of the pregnancy will be reported to the Sponsor and to Merck without delay and within 24 hours to the Sponsor and within 2 working days to Merck if the outcome is a serious adverse experience (e.g., death, abortion, congenital anomaly, or other disabling or life-threatening complication to the mother or newborn).

The study investigator will make every effort to obtain permission to follow the outcome of the pregnancy and report the condition of the fetus or newborn to the Sponsor. If a male subject impregnates his female partner the study personnel at the site must be informed

RUTGERS | eIRB  
APPROVED

Page 36 of 77  
IRB ID: Pro20170001392  
Approval Date: 2/22/2023  
Expiration Date: 5/10/2023

immediately and the pregnancy reported to the Sponsor and to Merck and followed as described above and in Section 7.2.2.

#### 5.5.4 Use in Nursing Women

It is unknown whether pembrolizumab is excreted in human milk. Since many drugs are excreted in human milk, and because of the potential for serious adverse reactions in the nursing infant, subjects who are breast-feeding are not eligible for enrollment.

#### 5.6 Subject Withdrawal/Discontinuation Criteria

Subjects may withdraw consent at any time for any reason or be discontinued from the trial at the discretion of the investigator should any untoward effect occur. In addition, a subject may be withdrawn by the investigator or the Sponsor if enrollment into the trial is inappropriate, the trial plan is violated, or for administrative and/or other safety reasons. Specific details regarding discontinuation or withdrawal are provided in Section 7.1.4.

A subject must be discontinued from the trial for any of the following reasons:

- The subject or legal representative (such as a parent or legal guardian) withdraws consent.
- Confirmed radiographic disease progression  
*Note:* For unconfirmed radiographic disease progression, please see Section 7.1.2.5.4 A subject may be granted an exception to continue on treatment with confirmed radiographic progression if clinically stable or clinically improved.
- Unacceptable adverse experiences as described in Section 5.2.1.2
- Intercurrent illness that prevents further administration of treatment
- Investigator's decision to withdraw the subject
- The subject has a confirmed positive serum pregnancy test
- Noncompliance with trial treatment or procedure requirements
- The subject is lost to follow-up
- Completed 24 months of uninterrupted treatment with pembrolizumab or 35 administrations of study medication, whichever is later.

*Note: 24 months of study medication is calculated from the date of first dose. Subjects who stop pembrolizumab after 24 months may be eligible for up to one year of additional study treatment if they progress after stopping study treatment provided they meet the requirements detailed in Section 7.1.5.5*

RUTGERS | eIRB  
APPROVED

IRB ID: Pro20170001392  
Approval Date: 2/22/2023  
Expiration Date: 5/10/2023

- Administrative reasons

The End of Treatment and Follow-up visit procedures are listed in Section 6.0 (Protocol Flow Chart) and Section 7.1.5 (Visit Requirements). After the end of treatment, each subject will be followed for 30 days for adverse event monitoring (serious adverse events will be collected for 90 days after the end of treatment as described in Section 7.2.3.1). Subjects who discontinue for reasons other than progressive disease will have post-treatment follow-up for disease status until disease progression, initiating a non-study cancer treatment, withdrawing consent or becoming lost to follow-up. After documented disease progression each subject will be followed by telephone for overall survival until death, withdrawal of consent, or the end of the study, whichever occurs first.

